10. STATISTICAL PLAN

10.1. Sample Size

The sample size calculation was performed with the assumption (which was based on the observed results from a Phase I trial) that the difference in change from baseline between the active dose groups and the placebo group for LDL-C will be no less than 30 mg/dL, with a standard deviation of 20 mg/dL, using a Dunnet multiple t-test procedure for six comparisons.

Assuming about a 15% drop out rate, the sample size will be approximately 100 evaluable subjects total across the placebo groups and approximately 50 subjects in each of six ALN-PCSSC treatment groups. This sample size of at least 400 evaluable subjects will provide more than 90% power to detect a 30% reduction of LDL-C levels in at least one ALN-PCSSC dose group.

10.2. Randomization

Subjects will be screened and 480 eligible subjects will be randomized by the IWRS system: 60 subjects per each of six ALN-PCSSC treatment groups plus 120 subjects total across the placebo groups (20 subjects each to match each of the six drug groups). Treatment will be stratified by country and by current use of statins or other lipid-modifying therapies. Each subject will either receive either one or two injections on Day 1 only or a single injection on Day 1 and a second injection on Day 90 of blinded ALN-PCSSC or placebo.

10.3. General Statistical Considerations and Definitions

10.3.1. General Statistical Methods

All study-collected data will be summarized by treatment group using descriptive statistics, graphs, and/or raw data listings. Categorical variables will be summarized using counts and percentages. Percentages are based on the number of subjects in the analysis set for whom there are non-missing data, unless otherwise specified. Continuous variables, including changes from baseline, will be summarized using descriptive statistics (n, mean, standard deviation, median and interquartile range [first and third quartiles], minimum and maximum).

A Statistical Analysis Plan will be written after finalizing of the eCRF and before database lock. The specifications in this document will detail the implementation of all the planned statistical analyses in accordance with the principal features stated in the protocol.

Statistical analyses will be carried out using SAS statistical analysis software version 9.2 or higher (SAS Institute, Inc., Cary, North Carolina, US).

10.3.2. Analysis Population

The following populations will be used for data analyses and/or presentation.

10.3.2.1. Intent-to-Treat (ITT) Population

All subjects randomized into the trial. Treatment classification will be based on the randomized treatment. This population will be used to assess the randomness of treatment allocation.

10.3.2.2. Modified Intent-to-Treat (mITT) Population

All randomized subjects who receive at least one dose of study drug and have both the baseline and the 180 day follow-up LDL-C assessment. Treatment classification will be based on the randomized treatment. This will be the primary population for analysis of the primary and secondary endpoints.

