10.3.2.3. Per-Protocol (PP) Population

All mITT subjects who received all randomized treatments and the 180 day follow-up LDL-C assessment. The PP population will be finalized during a data review before database lock. This will be the supportive population for analysis of the primary and secondary endpoints.

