10.3.3. Analysis Windows and Baseline

The observational period for each subject includes the screening period (from Day -14 to Day -1), the EOS visit (Day 210 or withdrawal date). The time at which LDL-C levels have returned to >80% of baseline values will be the last observation. Any lab results collected after the last observation will not be included in the planned efficacy analysis. Safety events after the last observation, even if collected on the eCRF, will not be included in the planned statistical analysis. However, all data, including that reported after the defined observational period, will be included in the subject data listings.

Unless otherwise specified, for evaluations that are collected at multiple occasions prior to initiation of study drug, the last evaluation will be considered the "Baseline" evaluation for analysis.

Two samples for lipids and PCSK9 will be taken prior to initiation of study drug (one at screening and one prior to randomization on Day 1). The average value of the two samples will be used as the baseline evaluation.

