10.4. Statistical Analyses

10.4.1. Demographic and Background Characteristics

Subject demographics and baseline characteristics (including medical history) will be summarized by treatment group using the ITT, mITT, PP, and safety populations.

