5.3.2.3. Per-Protocol (PP) Population

All mITT subjects who received all randomized treatments and the 180 day follow-up LDL C assessment. The PP population will be finalized during a data review before database lock. This will be the supportive population for analysis of the primary and secondary endpoints.

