5.4. Statistical Analyses

5.4.1. Demographic and Background Characteristics

Subject demographics and baseline characteristics (including medical history) will be summarized by treatment group using the ITT, mITT, PP, and safety populations.

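### The Day 180 LDL-C condition on the mITT set also governs the secondary endpoints, so treated subjects without that value drop out of the final efficacy summaries at every other visit

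*Protocol*

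**What the plan says.** Protocol 10.3.2.2 limits mITT to randomized, dosed subjects who "have both the baseline and the 180 day follow-up LDL-C assessment", and adds: "This will be the primary population for analysis of the primary and secondary endpoints". SAP 5.3.2.2 has the same definition and the same role.

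The other populations do not widen this:

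- **PP.** SAP 5.3.2.3 starts from "All mITT subjects who received all randomized treatments" and repeats the Day 180 condition. Protocol 10.3.2.3 gives its role: "This will be the supportive population for analysis of the primary and secondary endpoints".
- **ITT.** Protocol 10.3.2.1: "This population will be used to assess the randomness of treatment allocation". Its only other stated use is the baseline tables, which Protocol 10.4.1 says are "summarized by treatment group using the ITT, mITT, PP, and safety populations".
- **Safety.** Assigned to the safety analyses (Protocol 10.3.2.4, SAP 5.3.2.4).

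Protocol 10.4.3.2 lists percentage change in LDL-C at eight visits as secondary endpoints: Day 90, then Days 14, 30, 60, 104, 120, 150 and 210. SAP 5.4.4.2 lists seven, without Day 104. None of these is Day 180. Some other secondary endpoints do include Day 180: the responder and threshold proportions and PCSK9 change.

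The interim analysis of lipids and PCSK9 (Protocol 10.4.3.3, SAP 2.5) takes every subject who completes Day 90. Missing values are not imputed and leave only the analysis they belong to (Protocol 10.3.4, SAP 5.3.4). Under Protocol 10.3.3, all data "will be included in the subject data listings".

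**The concern.** A summary at Day 30 or Day 90 should not depend on whether the subject was measured months later. Under the stated sets it does. A subject who stops attending after Day 120, or who misses only the Day 180 visit and returns at Day 210, contributes to no final efficacy summary at any visit, although the earlier or later values are valid.

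Three things are at stake. First, the estimates at the other visits are conditioned on a post-randomization measurement. Second, the Day 90 result, a named secondary objective in the protocol, can change population between interim and final. Both analyses feed dose selection (Protocol 10.4.3.3, SAP 5.4.4). Third, Protocol 4.4 presses for complete follow-up of everyone randomized, yet part of what that effort yields goes unused in the efficacy summaries.

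The condition is also unnecessary for the primary test. With no imputation, a subject without a Day 180 LDL-C cannot enter a Day 180 t-test whichever set is named.

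**Working it through.** **Step 1: trace one subject through the sets.** Take a randomized subject who is dosed, has a baseline and LDL-C and PCSK9 at Days 14 to 150 and Day 210, but has no Day 180 LDL-C.

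| Set | Member? | Stated use |
|---|---|---|
| ITT | yes | allocation check, baseline tables |
| mITT | no | primary set, primary and secondary endpoints |
| PP | no (subset of mITT) | supportive set, same endpoints |
| Safety | yes | safety analyses, baseline tables |
| Interim, Day 90 completers | yes | lipids and PCSK9 at the interim |

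The subject enters neither set that has a role in the final efficacy analysis.

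**Step 2: reproduce the plan's own numbers.** Inputs are 480 randomized, 60 per active group and 120 placebo (Protocol 10.2), and about 15% dropout leaving about 50 per active group, about 100 placebo and at least 400 in all (Protocol 10.1).

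- 480 × 0.85 = 408, or 51 per active group and 102 placebo. This agrees with the stated approximate figures.
- Loss at 15%: 480 − 408 = 72 (9 per active group, 18 placebo).
- Loss at the stated 400: 480 − 400 = 80, which is 80/480 = 16.7% (10 per active group, 20 placebo).
- Power for a 30 mg/dL difference, SD 20 mg/dL, 50 against 100, six Dunnett comparisons (alpha 0.05 assumed; two-sided critical value about 2.62): above 0.999. The plan's claim of more than 90% holds on its own inputs.

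**Step 3: size the loss at Day 90.** Assumptions: every planned dropout lacks a Day 180 LDL-C; a fraction f of them has a Day 90 value; loss is proportional across arms; the SD is common; placebo is pooled, as in the sample-size section. The documents give no value for f, so the range is shown.

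Let n be the subjects with Day 180 and m = n + f × lost. The inflation of the standard error of an active-placebo difference is

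sqrt[(1/n1 + 1/n2) / (1/m1 + 1/m2)].

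With 1:2 allocation and proportional loss this reduces to sqrt(m1/n1), and the SD cancels.

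| f | 72 lost: Day 90 values omitted | SE ratio | 80 lost: Day 90 values omitted | SE ratio |
|---|---|---|---|---|
| 0 | 0 | 1.000 | 0 | 1.000 |
| 0.25 | 18 | sqrt(53.25/51) = 1.022 | 20 | sqrt(52.5/50) = 1.025 |
| 0.50 | 36 | sqrt(55.5/51) = 1.043 | 40 | sqrt(55/50) = 1.049 |
| 0.75 | 54 | sqrt(57.75/51) = 1.064 | 60 | sqrt(57.5/50) = 1.072 |
| 1 | 72 | sqrt(60/51) = 1.085 | 80 | sqrt(60/50) = 1.095 |

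**Step 4: put it on the planning scale.** Assume the planning SD of 20 mg/dL also holds at Day 90.

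- 72 lost, f = 0.25: 20 × sqrt(1/51 + 1/102) = 3.43 against 20 × sqrt(1/53.25 + 1/106.5) = 3.36, a difference of about 0.07 mg/dL.
- 80 lost, f = 0.75: 20 × sqrt(1/50 + 1/100) = 3.46 against 20 × sqrt(1/57.5 + 1/115) = 3.23, a difference of about 0.23 mg/dL.
- Ceiling (80 lost, f = 1): 3.46 against 20 × sqrt(1/60 + 1/120) = 3.16, about 0.30 mg/dL.

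**The case against.** The best defence is that little is lost. The protocol synopsis makes the secondary analyses descriptive, and a standard error larger by 0.07 to 0.23 mg/dL is small beside a planned difference of 30 mg/dL. Follow-up is required after treatment stops (Protocol 4.4 and 4.4.1), so stopping drug does not by itself remove anyone from mITT, and fewer than 72 subjects may be affected. All of this stands and keeps the point modest.

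Next, Day 90 is already covered without the Day 180 condition at the interim, the analysis expressly meant to help choose the dose. That stands for Day 90 only; the other visits have no such analysis. A reader might infer that the interim and final Day 90 sets contradict each other. They do not: they are two analyses with two stated sets, and the cost is comparability.

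Third, Protocol 10.3.1 and SAP 5.3.1 promise that all collected data will be summarized, plotted or listed, and mITT is called the primary set, not the sole one. A reader might infer from the set definitions that the omitted values can appear only in listings. That goes too far: this general promise leaves room for more, and hsCRP also falls under the laboratory summaries. But it names no efficacy population, so it does not restore these subjects to the mITT or PP summaries.

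Last, a fixed set helps when comparing visits. That is a real trade-off, but neither document gives it as the reason. Nor does mITT deliver a fixed set, since members may lack other visits and are then excluded there.

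**Conclusion.** The point holds as a matter of text. Treated subjects without a Day 180 LDL-C are left out of the final mITT and PP efficacy summaries at every other visit, and the final Day 90 result can rest on fewer subjects than the interim one. The change should be made, but the consequence is modest.

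The size is a Day 90 standard error about 2% to 7% larger than needed, with limits of 0% and 8.5% (72 lost) or 9.5% (80 lost). This rests on the assumptions in the working, chiefly that every planned dropout lacks Day 180 and that 25% to 75% of them have a Day 90 value.

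Two stronger readings are not supported. A reader might infer that the primary result is weakened and needs an added longitudinal or sensitivity model. This point gives no ground for that: the Day 180 test uses the same subjects with or without the condition, and its power is untouched. A reader might also infer that the secondary estimates are biased in a known direction. Conditioning on a later measurement makes bias possible, but the documents allow neither its size nor its direction to be derived.

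**What to change.** Amend Protocol 10.3.2.2 and SAP 5.3.2.2, and declare the change in SAP section 7, which now states that there are none:

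1. Limit the Day 180 LDL-C requirement to the primary Day 180 analysis. The Dunnett-adjusted t-tests stay as planned, on the same subjects.
2. For each visit-specific secondary endpoint, analyse as randomized every subject with at least one dose, a baseline and a value at that visit (Day 104 in two-dose subjects only). Show n by visit in each table.
3. For secondary endpoints not tied to one visit (time to return to 80% of baseline, attainment of lipid targets), use all treated subjects with a baseline and at least one post-baseline value.
4. Make the matching change to PP for the secondary endpoints (Protocol 10.3.2.3, SAP 5.3.2.3). Otherwise the supportive summaries keep the same condition.
5. State how the last-observation rule in Protocol 10.3.3 and SAP 5.3.3 applies to visit summaries. It excludes from the efficacy analysis laboratory results obtained after LDL-C has returned above 80% of baseline, so it bears on which visit values may be used.

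The cost is a few sentences in each document and no new data. The drawback is that the number of subjects will differ by visit, so comparisons across visits need to be read with the n beside them.

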10.3.2.3. Per-Protocol (PP) Population

All mITT subjects who received all randomized treatments and the 180 day follow-up LDL-C assessment. The PP population will be finalized during a data review before database lock. This will be the supportive population for analysis of the primary and secondary endpoints.

10.3.2.4. Safety Population

All subjects who received at least one dose of study drug. Treatment classification will be based on the actual treatment received. This will be primary population for the safety analyses.

10.3.3. Analysis Windows and Baseline

The observational period for each subject includes the screening period (from Day -14 to Day -1), the EOS visit (Day 210 or withdrawal date). The time at which LDL-C levels have returned to >80% of baseline values will be the last observation. Any lab results collected after the last observation will not be included in the planned efficacy analysis. Safety events after the last observation, even if collected on the eCRF, will not be included in the planned statistical analysis. However, all data, including that reported after the defined observational period, will be included in the subject data listings.

Unless otherwise specified, for evaluations that are collected at multiple occasions prior to initiation of study drug, the last evaluation will be considered the "Baseline" evaluation for analysis.

Two samples for lipids and PCSK9 will be taken prior to initiation of study drug (one at screening and one prior to randomization on Day 1). The average value of the two samples will be used as the baseline evaluation.

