After first study drug administration, the subject will be observed in the clinic for at least 4 hours post injection and will then be discharged. Subjects will return on Day 14 and Day 30 and then at monthly intervals for 6 months. Subjects whose LDL-C levels have returned to baseline levels and who have completed the study to Day 210 will be given the opportunity to enroll in a separate long-term extension study in order to collect long-term efficacy and safety data.

Any subjects in whom LDL-C levels have not returned to >80% of baseline values by Day 210 will continue to be followed on a monthly visit schedule in this study until either this level has been reached or until a maximum of Day 360 at which point they will be given the opportunity to enroll in the long-term extension study. At each visit, LDL-C levels, adverse events (AEs), serious adverse events (SAEs), concomitant medications, and safety laboratory assessments will be collected.

[figure not shown]
An interim analysis of lipids and PCSK9, unblinded by dose cohort only, will be prepared upon completion of Day 90 by the Statistical Reporting Organization. The interim analysis will be performed for all subjects completing Day 90 and these data will be used to help select the ALN-PCSSC dose for subsequent clinical trials.

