6.7. Additional Follow-Up Visits (Day 240 to Day 360)

Subjects in whom LDL-C levels have not returned to >80% of baseline values will return monthly (± 3 days) for Follow-Up Visits 10 to 14 (Days 240, 270, 300, 330, and 360) either until this level has been reached or until Day 360. The following procedures will be performed at these visits:

- HbA1c: At Day 270 and Day 360 (central)
- Central clinical laboratory (hematology, chemistry [including fasting glucose, liver and renal function, hsCRP and inflammatory markers IL6, IFN- γ and TNF- α], and coagulation testing)
- ADA at the last visit(central)
- Lipids/lipoproteins (LDL-C, HDL-C, total cholesterol, triglycerides) and PCSK9; non-HDL-C and very low-density lipoprotein-cholesterol [VLDL-C] will be derived from the lipid panel (central)
- Pregnancy test (local) at each additional follow-up visit until LDL-C has returned to > 80% of baseline values
- Concomitant medications

- AE reporting
- SAE reporting

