8.3. Procedure for Serious Adverse Event Reporting

NOTE: This procedure may need to be followed for reporting AESIs or Other Safety Related information as noted in [Section 8.1.5](#) and [Section 8.5](#).

All SAEs that occur during the designated study period (from randomization through the EOS visit) must be reported to the Sponsor's Global Pharmacovigilance Department (GPV) within 24 hours of awareness of the event using the provided study specific SAE/AESI Report Form. The completion and processing of the SAE/AESI Report Form should be per the instructions in the provided SAE/AESI Report Form completion guidelines. In addition to completing the SAE/AESI Report Form, each SAE/AESI must be entered on the appropriate page of the eCRF. Note: For subjects in whom LDL-C levels have not returned to >80% of baseline values by Day 210, SAEs will continue to be assessed at additional monthly follow-up visits (Day 240, Day 270, Day 300, Day 330, and Day 360) until the final observation.

When death occurs with an SAE, the cause of death must be reported as an SAE. "Fatal" will be reported as the outcome for these events.

The investigator must assess the causality for each SAE/AESI.

The Sponsor will contact the investigator, if necessary, to clarify any of the event information. The investigator should provide any follow-up information for the event to the Sponsor on an updated SAE/AESI report form as soon as it becomes available.

If the investigator is notified of a SAE/AESI that occurs post-study period, that he or she wishes to report to the Sponsor (eg, an event suspected to be causally related to study drug), the event should be reported through the process described above.

Where appropriate, if required by local regulations or procedures, the investigator should report these events to the Institutional Review Board (IRB)/Ethics Committee (EC) and/or national regulatory authority in addition to the Sponsor.

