5.3.3. Analysis Windows and Baseline

The observational period for the study includes screening period (from Day -14 to Day -1) to the EOS visit (follow-up Visit 8, Day 210 or withdrawal date). The time at which LDL-C levels have returned to >80% of baseline values will be the last observation. Any lab results collected after the last observation will not be included in the planned efficacy analysis. Safety events after the last observation, if collected on the eCRF, will not be included in the planned statistical analysis. However, all data, including safety events that were reported after the defined observational period, will be included in the subject data listings.

Unless otherwise specified, for evaluations that are collected at multiple occasions prior to initiation of study drug, the last evaluation will be considered the "Baseline" evaluation for analysis. Two PD samples for lipids and PCSK9 will be taken prior to initiation of study drug. The average of the two samples will be used as the baseline evaluation. If only one sample was collected, the collected sample will be used as baseline. If more than two samples were taken, then the average of the last two will be used as baseline.

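### The rule that ends observation when LDL-C is back above 80% of baseline has no earliest day; applied literally, it removes some Day 180 primary values because of the outcome

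*Protocol*

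**What the plan says.** Protocol 10.3.3 opens with the period of observation: "The observational period for each subject includes the screening period (from Day -14 to Day -1), the EOS visit (Day 210 or withdrawal date"). The next sentence sets the cut-off: "The time at which LDL-C levels have returned to >80% of baseline values will be the last observation". Two consequences follow. For efficacy, "Any lab results collected after the last observation will not be included in the planned efficacy analysis". For safety, "Safety events after the last observation, even if collected on the eCRF, will not be included in the planned statistical analysis". Data after the cut-off go to listings only.

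SAP 5.3.3 repeats the rule, also without a day, and SAP section 7 declares no change from the protocol. Protocol 10.3.4 and SAP 5.3.4 say that missing data are not imputed and drop out of the analysis concerned.

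Elsewhere the same threshold decides who stays on after the end-of-study visit. Protocol 3.1 says: "Any subjects in whom LDL-C levels have not returned to >80% of baseline values by Day 210 will continue to be followed". Protocol 6.7 sets monthly visits at Days 240 to 360 for these subjects. Protocol 8.2 and 8.3 continue event collection for them at "additional monthly follow-up visits (Day 240, Day 270, Day 300, Day 330, and Day 360) until the final observation".

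**The concern.** The cut-off depends on the outcome. Lipids are sampled through Day 210 in every subject, so someone who is back above 80% of baseline at Day 120 or Day 150 still has a Day 180 sample. Read literally, 10.3.3 excludes that sample from the efficacy analysis.

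In an active arm, the subjects removed are mainly those whose response is fading. In the placebo arm, they are those who dipped by chance and came back. Both losses push the placebo-adjusted difference in the drug's favour. The trial is meant to inform dose selection for later studies, and the regimens would be affected unequally. Counted safety follow-up would also stop at different times in different arms.

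**Working it through.** **1. The passages side by side**

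| Place | What it implies for a subject who falls and is back above 80% at Day 150 |
|---|---|
| Protocol 10.3.3 / SAP 5.3.3, last-observation sentence | Day 150 is the last observation; Day 180 is excluded |
| Protocol 10.3.3 / SAP 5.3.3, opening sentence | Observation runs to Day 210 or withdrawal |
| Protocol 10.3.2.2 / SAP 5.3.2.2 (mITT) | Subject is included, because a Day 180 LDL-C exists |
| Protocol 3.4 / SAP 5.4.4.2 | Subject should be counted in the proportion above 80% at Days 180 and 210 |

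The literal rule therefore conflicts with the sentence before it and with a secondary endpoint that needs the values it removes.

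**2. Worked subjects (LDL-C as % of baseline)**

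- 65, 60, 60, 65, 72, 83 at Days 14 to 150, then 88 at Day 180. The last observation is Day 150, so the Day 180 change of 88 − 100 = −12% is dropped.
- First back above 80% at Day 180. The value is kept, because the visit of return is itself the last observation.
- Never at or below 80%. Nothing has returned, so nothing is dropped.
- Two-dose subject at 70, 65, 72 and then 84 on Day 90, later 52 on Day 180. The last observation is Day 90, so every result after the second dose is dropped.

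**3. Inputs for an illustration**

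From Protocol 10.1: about 15% dropout, leaving about 100 evaluable placebo subjects and 50 per active group. This reproduces: 120 × 0.85 = 102, 60 × 0.85 = 51, 480 × 0.85 = 408. The point does not bear on the power calculation.

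The documents give no SD, between-visit correlation or time course on the percent-change scale. The following are assumptions:

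- Normal percent changes, equal correlation 0.5 to 0.8 between visits, SD 10 to 25 points.
- Placebo: mean 0 at every visit, half the subjects with a Day 104 visit.
- One dose, Days 14, 30, 60, 90, 120, 150, 180, 210: −35, −45, −48, −45, −40, −34, −28, −22.
- Two doses, with Day 104 added: −35, −45, −48, −45, −52, −54, −53, −50, −45.

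Above 80% of baseline means a change above −20%. Rule: drop Day 180 if any earlier post-dose visit was above −20% after a previous post-dose visit at or below −20%. Difference = mean of kept active Day 180 values − mean of kept placebo values. There were 400,000 simulated subjects per arm and scenario. Ranges below run over the correlation, and over both SDs in the first row.

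**4. Results**

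| SD | Placebo lost | One-dose lost | One-dose difference (true −28) | Two-dose lost | Two-dose difference (true −50) |
|---|---|---|---|---|---|
| 10–12 | 6–17% | 9–16% | −30.0 to −32.4 | 1–4% | −51.1 to −52.6 |
| 15 | 17–28% | 19–25% | −35.2 to −35.8 | 6–10% | −54.9 to −55.5 |
| 20 | 26–41% | 26–37% | −39.6 to −41.3 | 14–23% | −59.2 to −61.2 |
| 25 | 31–49% | 30–45% | −42.8 to −46.5 | 20–34% | −63.0 to −66.6 |

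At SD 20 and correlation 0.5, the kept one-dose mean is −34.4 and the kept placebo mean is +6.9: −34.4 − 6.9 = −41.3. So about half of the shift comes from each arm.

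Also at SD 20:

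- The one-dose share above 80% at Day 180 falls from 0.34 to about 0.2.
- Mean counted safety follow-up to Day 210 is 156–176 days on placebo, 167–181 on one dose and 179–192 on two doses.
- A weaker two-dose course (true −34 at Day 180) loses 32–52% and reads −44.6 to −48.1.

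**5. A second variance model**

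With between-subject SD 10–15, within-subject SD 5–15 and a one-dose mean near −30 at Day 180, placebo loses 0.1–40% and the one-dose arm 7–38%. The arm mean moves from −29.9 to −30.7 at the mild end and from −29.2 to −34.6 at the other. The direction is the same; the size can be small.

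**6. Rule limited to visits after Day 210**

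No Day 180 value is removed, so the loss and the bias are both zero.

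**The case against.** The best reply is that the intent is clear. Ending observation at Day 120 contradicts the opening sentence of the same paragraph. Both schedule tables attach the threshold to the additional follow-up column, Days 240 to 360. Protocol 3.1, 6, 6.7, 8.2 and 8.3 and SAP 5.4.4.2 use it for subjects not back by Day 210. SAP 2.4 lists return above 80% alongside the completed end-of-study procedures as a condition for finishing, so it adds to that visit and does not replace it. All of this stands as evidence of intent. But those passages say who attends extra visits, when participation ends, or what an endpoint is. None limits the exclusion rule itself.

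It is also fair that the size rests wholly on assumed inputs, and that a sustained two-dose response may lose almost nothing. That stands too.

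Three stronger readings are tempting, and the documents do not support them:

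- *The sponsor plans to discard Day 180 values.* The context points the other way.
- *Any post-dose value above 80% ends observation, which would nearly empty the placebo arm.* This strains the word returned: a subject who never fell has not returned.
- *The SAP closes observation at Day 180, because it calls the end-of-study visit follow-up Visit 8 while its Table 2 has FU8 at Day 180.* Day 210 is printed beside the label ("to the EOS visit (follow-up Visit 8, Day 210 or withdrawal date"), so this is an editorial slip.

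**Conclusion.** The point holds as a conditional defect in the wording. The missing day limit is certain in both documents. If the sentence is programmed as it stands, values leave the primary analysis because of the outcome, and the secondary proportions and counted safety follow-up are distorted as well. The overstatement of effect appeared in every scenario run.

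Its size is not established. In the first model it ranged from about 2 points (−30 against −28) to about 18 points (−46.5 against −28) for a waning one-dose course, depending on an SD, correlation and time course that the documents do not give. Under the reading that the context favours, there is no bias. It should be fixed because an analysis rule should not leave that choice to the programmer.

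**What to change.** In Protocol 10.3.3 and SAP 5.3.3, replace the last-observation sentence and the two exclusion sentences with text to this effect:

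> All efficacy results (lipids, lipoproteins, apolipoproteins, hsCRP, PCSK9), all safety laboratory values and all safety events through the EOS visit (Day 210 or withdrawal) enter the planned analyses for every subject, whatever the LDL-C level. The >80% cut-off applies only to subjects in additional follow-up after Day 210; their data are included through their final additional visit (return to >80% of baseline, or Day 360). Later data are listed only.

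This also supplies an end point for subjects who reach Day 360 without returning, for whom the present sentence defines none. As an editorial correction, make the visit number for Day 210 in SAP 2.4 and 5.3.3 agree with SAP Table 2 (FU9).

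The cost is wording only. The samples and events through Day 210 are already collected in all subjects, and no visit or procedure changes.
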